7. RFS
8. Proportion of subjects who transition to HSCT
9. Subjects who achieve RBC and/or platelet TI during the 8-week period after enrollment
10. PK parameters:  $C_{max}$ ,  $T_{max}$ , AUC, oral  $V_d/F$ , oral clearance (CL/F) and elimination  $T_{1/2}$  of APR-548 in the absence and presence of azacitidine.

11. PK parameters:  $C_{max}$ ,  $T_{max}$ , AUC,  $T_{1/2}$  of APR-548 and the metabolites M8 (reduced MQ-glutathione adduct), M10 (reduced MQ-cysteine adducts), MQ water adducts (MQ-H2O) and MQ glutathione adducts (MG-GSH).

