### 3.2 Secondary Objectives

1. To assess preliminary clinical activity of APR-548 administered in combination with azacitidine.
  - a. Rate of CR
  - b. Duration of CR (DOCR)
  - c. ORR
  - d. Duration of ORR
  - e. Rate of and time to development of AML transformation, as defined by WHO criteria
  - f. OS
  - g. Relapse-free survival (RFS)
  - h. Rate of transition to hematopoietic stem cell transplant (HSCT)
  - i. Rate of red blood cell (RBC) and/or platelet transfusion independence (TI) for 8 weeks
2. To characterize PK of APR-548 after single and multiple dosing when given orally (p.o.)
3. To evaluate the PK drug-drug interaction between APR-548 and azacitidine.

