#### **4.7 Inclusion Criteria**

1. Provision of signed and dated, written informed consent prior to any study specific procedures.
2. Documented diagnosis of *TP53*-mutant MDS, according to WHO criteria that is previously untreated and meets IPSS-R classification of intermediate, high, or very high risk disease, or *TP53*-mutant MDS that is relapsed and/or refractory to prior treatments. Eligible *TP53* mutations are defined in [Appendix VII](#).
3. Adequate organ function as defined by the following laboratory values:
  - a. Creatinine clearance  $\geq 60$  mL/min (by Cockcroft-Gault method, [Appendix I](#)),
  - b. Total serum bilirubin  $\leq 1.5 \times$  upper limit of normal (ULN), unless due to Gilbert's syndrome or MDS organ involvement,
  - c. Alanine aminotransferase (ALT) and aspartate aminotransferase (AST)  $\leq 2.5 \times$  ULN, unless due to MDS organ involvement.
4. Age  $\geq 18$  years at the time of signing the informed consent form.
5. Eastern Cooperative Oncology Group (ECOG) performance status of 0, 1 or 2 ([Appendix II](#)).
6. Projected life expectancy of  $\geq 12$  weeks.
7. Clear ocular media and adequate pupil dilation to permit fundus examination and retinal imaging.
8. Female subjects must be surgically sterile, postmenopausal (for at least 1 year), or have negative results for a pregnancy test at screening, on a serum or urine sample obtained within 7 days prior to initiation of study treatment.
9. Heterosexual female subjects of childbearing potential must agree to use adequate contraception or practice sexual abstinence as the preferred and usual lifestyle of the subject during the study and for up to 90 days after study treatment discontinuation. Adequate contraception is defined by the concomitant use of 2 effective methods of contraception, which can be comprised of two barrier methods, or a barrier method plus a hormonal method or an intrauterine device that meets  $<1\%$  failure rate for protection from pregnancy in the product label ([Appendix III](#)). Females of non-childbearing potential are those who are postmenopausal greater than 1 year or who have had a bilateral tubal ligation or hysterectomy or bilateral oophorectomy. Female subjects must refrain from egg cell donation while on study treatment and for at least 90 days after the last dose of APR-548 or azacitidine, whichever is longer.

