**Table 12. Schedule of assessments**

Assessments	Screening a	Safety Run-In (APR-548 Monotherapy) b										APR-548 + Azacitidine Combination												End of treatment x	Long-term follow-up y
												Cycle 1 (Safety Run-In)						Cycle 2				Cycles 3+			
		D1	D2	D3	D4	D5	D8	D15	D21	D28	D1	D2 - 7	D8	D15	D22	D1 c	D2 - 7	D8	D15	D1 d	D2 - 7	D15 e			
Informed consent	x																								
Mutant TP53 confirmation f	x																								
Medical history g	x																								
Physical examination h	x	x							x	x	x					x	x	x			x			x	
Vital signs h	x	x	x	x	x				x	x	x	x	x	x	x	x	x	x	x	x	x	x	x	x	
Height i	x																								
Weight	x	x							x	x	x					x	x	x			x			x	
ECOG performance status	x	x						x	x	x	x					x	x	x			x			x	
APR-548 j		x	x	x	x						x j	x				x j	x			x	x				
Azacitidine k											x	x				x	x			x	x				
Disease assessment l	x							x												x				x	
Hematology m	x	x					x		x	x	x		x	x	x	x	x	x	x	x	x	x	x	x	
Serum chemistry n	x	x					x		x	x	x		x	x	x	x	x	x	x	x	x	x	x	x	
Creatinine clearance o	x	x				x		x	x	x	x		x	x	x	x	x	x	x	x	x	x	x	x	
Coagulation profile p	x								x				x			x									
Pregnancy test q	x								x						x				x				x	x	
ECG r	x	x	x		x	x					x	x				x				x			x	x	
APR-548 PK sample s	x	x		x	x						x	x				x				x					
Azacitidine PK sample s											x	x													
PBMC/BMMC sample collection t	x					x													x			x			
Blood sample for PD markers u		x	x		x	x					x	x													
Bone marrow biopsy (optional)					x																				
Ophthalmological evaluation v	x						x		x				x	x				x	x	x	x v	x			
Clinical safety assessment w		Starting at the time of study treatment initiation through 30 days after last dose																							
Concomitant medications		Reviewed throughout study																							
Transfusion log		From 8 weeks prior to enrollment to end of treatment/off treatment																							
Survival																								x	

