## 7.2 Efficacy Assessments

### 7.2.1 Complete Remission Rate

CR rate will be summarized for the safety and efficacy-evaluable (EE) subjects as the proportion (%) of subjects with CR per the IWG 2006 criteria ([Appendix V](#)). In addition to presenting the CR rate, its associated exact 95% CI will also be presented.

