### 7.2.6 Rate of AML Transformation, Transition to HSCT, and Transfusion Independence

Rate of AML transformation, transition rate to HSCT, and rate of RBC TI and/or platelet TI will be analyzed using the similar methodology as CR rate.

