## 8.2 Analysis Populations

Safety population: Subjects will be evaluable for safety if they receive at least one dose of APR-548. The safety population will be the primary analysis population used for all analyses such as subject disposition, subject demographics, exposure, safety parameters and efficacy parameters. The safety population will be the primary analysis population for efficacy.

EE population: All subjects who complete at least one treatment cycle of APR-548 and who have at least one post-treatment clinical response assessment. The EE population will be the secondary analysis population for efficacy.

PK population: Subjects will be evaluable for PK if at least one sample for PK evaluation has been obtained.

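### The transfusion-independence rate has no baseline-dependence condition and, by cross-reference, an all-subject denominator, so it can be substantial when no subject converts

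*Combined protocol and SAP*

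**What the plan says.** - **Objective (Section 3.2).** Among the measures of clinical activity of the combination: "Rate of red blood cell (RBC) and/or platelet transfusion independence (TI) for 8 weeks".
- **Endpoint (Section 8.3.2, item 9, and the synopsis).** "Subjects who achieve RBC and/or platelet TI during the 8-week period after enrollment". It states no baseline condition and no denominator.
- **Analysis (Section 7.2.6).** "rate of RBC TI and/or platelet TI will be analyzed using the similar methodology as CR rate". Section 8.6 does not mention TI.
- **The method it points to (Section 7.2.1).** "CR rate will be summarized for the safety and efficacy-evaluable (EE) subjects as the proportion (%) of subjects with CR", with an exact 95% confidence interval.
- **Population (Section 8.2).** "The safety population will be the primary analysis population for efficacy", and "Subjects will be evaluable for safety if they receive at least one dose of APR-548". The EE population is secondary.
- **Eligibility (Sections 4.7 and 4.8).** The disease must be *TP53*-mutant MDS that is either "previously untreated and meets IPSS-R classification of intermediate, high, or very high risk disease" or relapsed or refractory. Transfusion need is not a criterion.
- **Data (Table 12).** The transfusion log runs "From 8 weeks prior to enrollment to end of treatment/off treatment". No text links it to TI. Appendix V does use a pre-treatment transfusion count, but only for erythroid haematological improvement.

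**The concern.** A response rate of this kind is meant to show how many subjects who needed transfusions stopped needing them. As written, two different groups can enter the numerator without any change in status. One is subjects who never needed the product. The other, if 'and/or' is read as either product, is red-cell-dependent subjects who never needed platelets. The rate then depends on who was enrolled as well as on what treatment did.

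Section 8.0 has data presented by dose level. In a cohort of 6, one subject's baseline status moves the rate by 1/6, or about 17 percentage points. Differences between dose levels could therefore come from case mix and be taken for activity.

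**Working it through.** **Denominator.** The endpoint gives none. Section 7.2.6 refers to the CR-rate method, Section 7.2.1 makes that a proportion of safety and EE subjects, and Section 8.2 makes the safety population primary. This is the only route the protocol provides.

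**Size of the denominator.** The synopsis gives 6 cohorts × 6 subjects + 10 = 46, which agrees with the stated maximum of 46. The documents give no target TI rate and no baseline dependence rate, so the rates below are assumptions.

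**Formulas.** Let r and p be the proportions dependent at baseline on red cells (RBC) and platelets. With no conversions and nobody worsening:
- RBC TI = 1 − r
- either-product TI = 1 − P(dependent on both)
- P(dependent on both) = r × p if the two are independent, or the smaller of r and p if one is nested in the other

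**Example, r = 0.50 and p = 0.20.** RBC TI = 1 − 0.50 = 50%. Either-product TI = 1 − 0.50 × 0.20 = 90% (independent) or 1 − 0.20 = 80% (nested). Rounded to whole subjects out of 46, with exact 95% intervals:

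| r / p | RBC TI | Either product, independent | Either product, nested |
|---|---|---|---|
| 50% / 20% | 23/46 = 50.0% | 41/46 = 89.1% (76.4–96.4) | 37/46 = 80.4% (66.1–90.6) |
| 70% / 40% | 14/46 = 30.4% | 33/46 = 71.7% (56.5–84.0) | 28/46 = 60.9% (45.4–74.9) |
| 90% / 60% | 5/46 = 10.9% | 21/46 = 45.7% (30.9–61.0) | 18/46 = 39.1% (25.1–54.6) |

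Over r from 30% to 90%, p from 10% to 60%, and overlap from minimal to nested, the either-product rate runs from 39% to 100%. The true conversion rate is 0% throughout.

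**Worsening on treatment.** Suppose 40% of subjects independent of each product at baseline become dependent on it (assumption). From r = 0.50 and p = 0.20, dependence becomes 0.50 + 0.50 × 0.40 = 0.70 and 0.20 + 0.80 × 0.40 = 0.52. RBC TI falls from 50% to 30%. Either-product TI falls from 90% to 1 − 0.70 × 0.52 = 64% (independent), or from 80% to 1 − 0.52 = 48% (nested).

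**If only conversion counts.** With conversion rate c among dependent subjects, the all-subject rate is c × r. At r = 0.50 it is half of c.

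**With a product-specific denominator.** At 50% / 20% with no conversions, RBC conversion is 0/23 = 0% (0–14.8) and platelet conversion 0/9 = 0% (0–33.6).

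**Window.** The objective asks for independence lasting 8 weeks, with no fixed start. The endpoint fixes the 8 weeks that follow enrolment. For a subject who passes through the monotherapy run-in, about 28 of those 56 days come before azacitidine starts, although the objective concerns the combination. A dependent subject who becomes independent later meets the objective but not the endpoint.

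**The case against.** Several counter-arguments have force.

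- **The denominator is inferred.** 'Similar methodology' could mean only a proportion with an exact interval. That is possible, but no other TI denominator is given, so an analyst following the text would reach the safety population.
- **'Achieve' suggests a change of status.** Nothing defines it so. If it does mean conversion, a high rate without converters cannot occur. A reader might infer that every reading gives a wrong proportion; that goes too far. Converters over all treated subjects is a valid, conservative quantity, and the overall response rate already counts haematological improvement, which needs a pre-treatment cytopenia, over the same population. What remains is the dilution.
- **Section 7.2.6 may mean two separate rates.** It names TI once for each product. On that reading the either-product figures disappear, but RBC TI is still 50% with no conversions at 50% dependence.
- **The magnitudes are assumed.** They rest on baseline rates that the protocol does not give and on nobody worsening, while its toxicity tables plan for new grade 3 or 4 haematologic toxicity. This stands.
- **A baseline-referenced measure already exists.** Erythroid improvement uses the previous 8 weeks. This limits the risk of misjudging activity but does not define TI.

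**Conclusion.** The concern holds in a limited form. By cross-reference, the TI rate is a proportion of all safety (and EE) subjects, with no baseline-dependence condition and an ambiguous two-product criterion. Read literally, it can be substantial with no conversions. At an assumed 50% red-cell and 20% platelet dependence with nobody worsening, it is 50% for red cells and 80% to 90% for either product. Heavier overlapping dependence takes the either-product figure down to 39% in the range examined, and worsening lowers it further. If conversion is meant, the rate is valid but diluted.

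A reader might infer that the reported rate will be very high, or that it will mainly count subjects who never needed transfusions. The documents support neither, because both need baseline rates that are not given and one particular reading of the endpoint. Nor is dose selection at risk: TI is a secondary descriptive endpoint, and dose-limiting toxicity and recommended phase 2 dose decisions do not use it.

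**What to change.** In the synopsis, Section 7.2.6 and Section 8.3.2:

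1. Define baseline dependence separately for red cells and platelets from the existing log of the 8 weeks before enrolment. State how much transfusion counts as dependence, since a rule of any transfusion would include a single isolated unit.
2. Report conversion to independence separately for each product, among subjects dependent on that product at baseline, with exact 95% intervals.
3. Report maintenance of independence separately, among subjects independent of that product at baseline.
4. Drop the either-product rate, or require independence from both products.
5. Reconcile the 8-week duration in Section 3.2 with the fixed post-enrolment window in Section 8.3.2, and state how subjects with less than 8 weeks of follow-up are counted.

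No new data, visits or subjects are needed. The cost is smaller denominators and wider intervals (in the example, 23 and 9 subjects in place of 46), and probably a less favourable figure. Because the text is in the protocol, the change also needs a sponsor-approved modification under Section 9.3.

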### 8.3.3 Exploratory

1. PD markers of APR-548 may be explored using flow cytometry and molecular techniques including, but not limited to, markers of apoptosis and proliferation
2. Exploratory analyses of molecular markers of response may include: *TP53* VAF by NGS, mutations and VAF of other genes by NGS, and gene and protein expression

## 8.4 Safety Stopping Criteria

The study will implement the following stopping criteria:

- Any death within 30 days from the first dose of APR-548.
- A medically equivalent serious AE experienced by >1 subject within the first 30 days of study treatment (monotherapy and 1st cycle of combination treatment).
- Any > Grade 3 AE experienced by >2 subjects within the first 30 days of study treatment.
- Any  $\geq$  Grade 3 ocular associated AE that does not return to  $\leq$  Grade 1 or baseline within 7 days.

If a stopping criterion is met, enrollment will be temporarily suspended until the DRT has performed a prompt cumulative review of safety data and the circumstances of the event in question, to determine whether dosing and/or the protocol should be modified.

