Treatment Plan	
Treatment will be administered on an outpatient basis but may be administered in the inpatient setting for subjects who are hospitalized and meet criteria for treatment. No investigational or commercial agents or therapies other than those described below may be administered with the intent to treat the subject's disease under study.
 
In the 28-day safety run-in period, APR-548 will be given p.o. QD on Days 1 through 4. Following discussions with the DRT, the schedule of APR-548 may be modified, including multiple daily and weekly doses. Following the 28-day safety run-in period, subjects proceed to the combination portion.
 
In the combination portion, APR-548 will be given p.o. QD on Days 1 through 4 of each 28-day cycle. Azacitidine will be given at the standard dose of 75 mg/m^2 over 7 consecutive days (Days 1-7) as a s.c. injection or i.v. infusion. Following discussions with the DRT, the schedule of APR-548 may be modified, including multiple daily and weekly doses.
 
Subjects in the 28-day safety run-in periods will be followed for at least 28 days before the safety of each cohort can be fully assessed and decisions made for dose

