## 4.0 TRIAL DESIGN

### 4.1 Overview of Trial Design

This is an open-label FIH phase 1 clinical trial that will assess safety, PK, and clinical activity of p.o. administered APR-548 in combination with azacitidine for the treatment of *TP53*-mutant MDS.

Treatment will be administered on an outpatient basis but may be administered in the inpatient setting for subjects who are hospitalized and meet criteria for study treatment. No investigational or commercial agents or therapies other than those described below may be administered with the intent to treat the subject's disease under study.

The study is guided by a 3+3 dose escalation of APR-548 in the safety run-in monotherapy and the safety run-in combination therapy portions.

APR-548 will initially be given p.o. QD during Days 1 – 4 of a 28-day safety run-in period. The first 3 subjects enrolled on each dose level will be evaluated for a 28-day DLT safety follow-up period prior to enrolling additional subjects on that dose level or prior to dose escalation. If no DLT is observed, subjects will proceed to the safety run-in combination therapy portion with APR-548 in combination with azacitidine administered s.c. or i.v. at the standard dose of 75 mg/m^2 on Days 1-7 of the 28-day cycle. The first 3 subjects on each dose level of the combination with APR-548 and azacitidine will be evaluated for a 28-day DLT safety follow-up period prior to enrolling additional subjects on that dose level or prior to dose escalation with the combination treatment.

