### Footnotes to schedule of assessments

- a. All screening/baseline assessments are performed within 28 days prior to the start of study treatment. In the event that a visit or test cannot be scheduled on the exact visit day, a window of  $\pm 3$  days is allowable.
- b. A window of  $\pm 1$  day is allowable for visits during the safety run-in (APR-548 monotherapy) period.
- c. A window of  $\pm 2$  days is allowable for this visit.
- d. After the first cycle, Day 1 assessments of subsequent cycles are to be done within 3 days prior to next cycle drug administration.
- e. A window of  $\pm 5$  days is allowable for this visit.
- f. Can be confirmed using archived sample.
- g. Full medical history is obtained at screening for safety and eligibility purposes; this will include any clinically significant findings from 28 days prior to screening date.
- h. Physical exam and vital signs (including blood pressure, heart rate, respiration rate and temperature) are completed for safety purposes and clinically significant items are recorded as AEs where appropriate. Vital signs are collected on days of APR-548 administration.
- i. Can be recorded historically from up to 1 year prior to informed consent.
- j. APR-548 is administered p.o. on Days 1–4 of each 28-day cycle. Cycle 1 Day 1 of the combination treatment may proceed following ophthalmic evaluation performed by retina specialist to ensure there are no retinal or optic nerve associated AEs, and to evaluate for other potential ocular AEs.
- k. Azacitidine is administered s.c. or i.v. over 7 consecutive days, on Days 1–7 of each 28-day cycle. SC route is preferred but may be given i.v. at the investigator's discretion. The same route should be maintained over the 7-day treatment period (whichever route of administration is used on Day 1; the same route should be followed on all other days).

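### The death stopping criterion closes at about Day 2 of combination Cycle 1, so a single later death in that safety run-in does not by itself suspend enrolment

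*Combined protocol and SAP*

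**What the plan says.** Section 8.4 and the synopsis (Statistics) give the same four stopping criteria. If any is met, enrolment is paused while the DRT promptly reviews cumulative safety data.

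- **Death:** "Any death within 30 days from the first dose of APR-548". One death is enough.
- **SAE:** "A medically equivalent serious AE experienced by >1 subject within the first 30 days of study treatment". A parenthesis then names monotherapy and the first "cycle of combination treatment".
- **Above Grade 3 AE:** more than two subjects, in the first 30 days of study treatment. No parenthesis follows.
- **Ocular:** one Grade 3 or worse ocular event that has not recovered within 7 days. No calendar window is given.

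On timing, Section 4.1 says "APR-548 will initially be given p.o. QD during Days 1 – 4 of a 28-day safety run-in period". The synopsis (Treatment Plan) continues "Following the 28-day safety run-in period, subjects proceed to the combination portion", and "In the combination portion, APR-548 will be given p.o. QD on Days 1 through 4 of each 28-day cycle". The synopsis and Section 6.5 treat combination Cycle 1 as a safety run-in, and Section 5.1.3 applies the 28-day DLT definition to it.

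**The concern.** The trial has two declared 28-day safety run-ins, but the clock of the death criterion starts only once, at the beginning of the first. Nothing restarts it when azacitidine is added. The most serious event is thus covered for almost none of the run-in that addresses the trial's title question. The SAE criterion directly below it names both periods, and the documents available for review do not explain the difference.

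At stake is a prompt, automatic look at the data. Monotherapy escalation may run ahead of the combination (Section 4.1; synopsis, Treatment Plan). New subjects could therefore keep entering monotherapy after a combination death without any rule requiring a pause.

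**Working it through.** **1. Inputs**

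- First APR-548 dose: study Day 1, in the monotherapy run-in (Section 4.1).
- Run-in length 28 days, so Cycle 1 Day 1 is study Day 29 if there is no delay.
- Cycle length 28 days, so Cycle 1 is study Days 29 to 56.
- Run-in visits: a window of plus or minus 1 "day is allowable for visits during the safety run-in (APR-548 monotherapy) period" (footnotes to Table 12).
- Condition before combination: "Cycle 1 Day 1 of the combination treatment may proceed following ophthalmic evaluation performed by retina specialist" (same footnotes). Waiting for this can delay Cycle 1 and so shorten the overlap.
- Median overall survival in *TP53*-mutant disease: best estimate 8 months, range 5 to 9 (Section 2.2). Used only for step 4.
- Maximum sample size: 6 × 6 + 10 = 46, which reproduces the synopsis figure.

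**2. Overlap of the death window with Cycle 1**

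Covered days = max(0, last covered study day − Cycle 1 Day 1 + 1).

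| Start of Cycle 1 | Last covered day 30 | Last covered day 31 (30 elapsed days) |
|---|---|---|
| Day 28 (1 day early) | 3 | 4 |
| Day 29 (nominal) | 30 − 29 + 1 = **2** | 3 |
| Day 30 | 1 | 2 |
| Day 31 | 0 | 1 |
| Day 32 or later | 0 | 0 |

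Nominal cover is 2/28 = 7.1%, leaving 26 days uncovered. The window closes on the second of the seven azacitidine days (study Days 29 to 35).

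**3. Would another criterion respond to one death on, say, Cycle 1 Day 10 (study Day 38)?**

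- SAE criterion: death is an SAE (Section 7.1.2.4), but a medically equivalent SAE in a second subject is needed.
- Above Grade 3 criterion: three or more subjects are needed, whatever its window.
- Ocular criterion: not relevant unless the event is ocular.

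So one death alone meets none of them. The reach of the middle two is also unclear. Thirty days of study treatment cannot contain monotherapy plus the first combination cycle, which together run 28 + 28 = 56 days.

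**4. What covering Cycle 1 would cost**

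Assume exponential survival from the first dose and 30.4375 days per month. With an 8-month median (243.5 days), S(t) = 0.5^(t/243.5).

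- P(death on Days 31 to 56) = S(30) − S(56) = 0.9181 − 0.8526 = 0.0655.
- Over 46 subjects: 46 × 0.0655 = 3.0 deaths.
- At least one such death among 6 subjects: 1 − (1 − 0.0655)^6 = 33%.
- Medians of 9 and 5 months give 0.0590 and 0.0974, hence 2.7 and 4.5 deaths over 46, and 31% and 46% among 6 subjects.

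**The case against.** The strongest reply is that other safeguards reach a combination death.

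- A fatal non-haematological event in Cycle 1 is a DLT unless it is clearly and solely due to the disease, and two DLTs in a cohort end escalation (Sections 4.1 and 5.1.3).
- The DRT reviews safety data for each cohort in both portions.
- Section 4.1 holds further enrolment at a combination dose level until the first three subjects complete 28 days.
- SAEs are reported within 24 hours, and the Medical Monitor reviews all of them (Sections 7.1.2.6 and 7.1.2.7).

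All of this stands. A reader might infer that a combination death escapes DRT review; the documents do not support that. But none of these safeguards suspends enrolment after one death. A single DLT among three subjects leads to three more being enrolled, and DRT meetings are timed by accrual.

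A reader might also infer that no death on the combination triggers suspension. That goes too far. A death on Cycle 1 Day 1 or 2 nominally does, and a fatal SAE that matches another subject's SAE can meet the second criterion. Nor should the above Grade 3 criterion be said to share the death window. It counts from study treatment rather than from the first APR-548 dose, and the parenthesis in the SAE criterion attaches Cycle 1 to that same phrase, so it may already reach Cycle 1.

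Finally, tying a single-death trigger to first exposure to a first-in-human agent is a coherent choice, and background mortality would produce pauses unrelated to drug. Parts of the combination rationale, the risk section and the escalation text are redacted, and the separate safety plan is not supplied, so intent cannot be judged. This argues for a statement of intent, not for leaving the windows unreconciled.

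**Conclusion.** The point holds as a specific gap in an automatic trigger. For subjects on the described sequence, the death criterion covers nominally 2 of 28 Cycle 1 days (0 to 4 across the counting and timing cases in the table). A single death after about Cycle 1 Day 2 does not by itself suspend enrolment or prompt the review tied to suspension.

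This rests on day-counting from the protocol's own schedule and needs no survival assumption. It would not apply to any of the up to 10 additional RP2D subjects who started directly on the combination, since 30 days from their first dose would span all of Cycle 1. The documents do not say whether they do.

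The mortality figures describe the cost of wider cover, not treatment-related deaths missed. They are probably high: 46 is a maximum, eligibility requires a projected life expectancy of at least 12 weeks, and the 8-month median includes oligoblastic AML, whereas this trial enrols subjects with under 20% blasts.

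**What to change.** Reconcile the windows in Section 8.4 and the synopsis with the two 28-day safety run-ins:

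- For each criterion, state when the clock starts, when it ends, and whether combination Cycle 1 is covered.
- Resolve the 30-day limit in the SAE criterion against its own parenthesis, and say whether the same meaning applies in the above Grade 3 criterion.
- If Cycle 1 deaths are deliberately outside the death criterion, say so and give the reason.
- State how the windows apply to any subject who enters without a monotherapy run-in.

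The editing cost is a line or so per criterion in two places. If the sponsor decides that Cycle 1 is covered, cover rises from 2 to 28 of 28 days. The price is some temporary pauses for disease-related deaths, about 3 over a full 46 subjects on the 8-month assumption and probably fewer.
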